do not show up to the first scheduled clinician visit will be considered enrolled and included in the primary analysis.

--Power Calculations--

For the following power calculations, we used an adjusted Type I error of 0.025 to account for two comparisons: 1) clinic-level nudges versus usual care, and 2) intensification for high-risk patients versus no intensification within practices where clinic-level nudges are provided. Based on retrospective data from our health systems, we will have 85% power to detect a 7-percentage point difference in the flu vaccine completion rate for comparison #1. This calculation assumed N=48 participating clinics across the two sites, an average cluster size of n=1385 patients, and an intracluster correlation (ICC) of 0.02. For comparison #2, we will have at least 99% power to detect a 2-percentage point difference even if the rate of vaccination in the high-risk group is 50%, the most conservative rate with respect to power. This calculation assumed 1:1 individual-level randomization of n=1000 high-risk patients within each of N=32 clinics that will be randomized to receive clinic-level nudges. These power calculations used combined retrospective data from Penn and UW to estimate the average number of patients per clinic and the number of high-risk patients who will be randomized. We expect to have greater power for both comparisons at the replication site which comprises more clinics and patients.

--Statistical Analysis--

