The primary analysis will fit generalized estimating equations (GEE) with a binary outcome indicating whether a flu vaccine was received during the PCP visit (primary). Following the intention-to-treat framework, patients who do not complete their first scheduled visit will contribute a primary outcome of zero, indicating a flu vaccine was not received during the PCP visit. We will also perform analyses based on a binary outcome that indicates whether a flu vaccine was received 3 months after the first scheduled visit, regardless of whether the visit was completed (secondary). An exchangeable working correlation will be specified at the clinic level for comparison #1 (evaluation of clinic-level nudges) and robust standard errors will be provided, clustered at the clinic level. An independence working correlation and robust standard errors without clustering will be used for comparison #2 (evaluation of individual-level nudges). In sensitivity analyses we will explore alternative specifications for the working correlation structure to examine robustness of parameter estimates and inference. In additional sensitivity analyses, we will censor patients with a PCP visit late in the intervention period (February/March) who are unlikely to complete a flu vaccine beyond March and will therefore not have a full 3 months to obtain a vaccine and examine completion rates among these patients.

We will examine effects of the interventions on overall rates of ordering. We will compare rates of ordering between the three intervention arms: 1) Control, 2) Clinic-level nudges only, and 3) Clinic-level nudges with intensification for high risk. We will fit a GEE with binary outcome indicating whether an order was signed or not. We will fit the model using the weighted and replicated approach¹³ to account for the fact that low-risk patients seen in the clinics that received nudges are consistent with both intervention arms 2) and 3). We will include terms for the main effects of clinic-level and individual-level nudges as well as their interaction. We will test the appropriate linear combinations of the parameters that correspond to pairwise differences between each of the three intervention arms. An independence working correlation with robust standard errors will be

used to account for uncertainty in the weight distribution due to variability in the empirical proportion of high- versus low-risk patients.

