BE IMMUNE: Behavioral Economics to IMprove and Motivate vaccination Using Nudges through the EHR

University of Pennsylvania

[name]

[name]

[name]

NCT#06057727

Statistical Analysis Plan

01/07/2025

Objectives

Our primary objective is to test the effectiveness of multicomponent, personalized EHR-based nudges to both clinicians and patients for increasing flu vaccination completion among eligible primary care patients.

Relevant Study Design Details

Randomization

Primary care clinics will be randomized 2:1 to either a nudge intervention or usual care arm using covariate-constrained randomization, stratified by health system (Penn, UW). For the clinic level randomization, the covariate-constrained randomization will aim to balance the distribution of clinician panel baseline flu vaccination completion rate, panel size, and panel risk. Panel size is defined as the number of patient visits from September 1, 2022 through February 28, 2023. Panel risk is defined as the proportion of a clinician's patients who meet at least one of the following criteria: age \geq 70 years, Non-Hispanic Black race, residence in lower income communities (lowest quartile according to zip code), or no documented history of flu vaccine in the year prior. Second, patients who have an eligible appointment at an intervention clinic and are identified as high-risk for not completing a flu vaccination will be further randomized using a 1:1 ratio at the patient level—stratified by clinic—to receive either an additional, intensification nudge (bi-directional texting) or the standard nudge intervention (standard text messaging).

Blinding

All investigators, statisticians, and analysts will be blinded during the randomization, intervention, and analysis phases. They will be unblinded at the end of the study analyses, after all outcomes have been obtained.

Outcomes

The primary outcome is flu vaccination completion during the first eligible primary care visit.

Secondary outcomes are flu vaccination completion within 3 months of the first eligible primary care visit and flu vaccination ordering. These patient-level outcomes will be coded as a 1 to indicate completion (or signed order) and 0 to indicate non-completion (or unsigned/cancelled order).

Statistical Analysis

The primary analysis for all primary and secondary outcomes will follow the intent-to-treat principle.

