where A_1 is an indicator of whether the patient was seen at an active (1) or control (-1) clinic; A_2 is an indicator of intensive (1) or standard (-1) text messaging (patients who were actually randomized will have only one value for A_2 , while replicated patients will have one 1 and one -1); $A_1 A_2$ is the interaction between the patient’s cluster assignment and their individual-level assignment(s); and X is a vector of all other covariates we want to control for which will at minimum include mean-centered versions of the three variables used in the constrained randomization procedure: 1) clinic size (number of patient visits); 2) baseline clinic risk (proportion of panel deemed high risk); and 3) baseline clinic completion rate (proportion of panel with completed flu vaccination).

We will specify an independence working correlation when fitting the primary GEE model.

Although we expect some amount of correlation amongst observations within clinic, the replicated subject observations should be treated as independent. Fortunately, estimates from GEE models are robust to misspecification of the working correlation structure, meaning they are consistent for the true values even when the working correlation is specified incorrectly. Furthermore, when correlation amongst observations within clinic is low, the efficiency of using an exchangeable working correlation is similar to or worse than when using an independent working correlation. Since we will randomize 45 clinics, we will not use a small cluster correction.² We will use this approach for both the primary and secondary outcome analyses. Given model (1) with effect coding (i.e., -1 and 1 for levels of A_1 and A_2), we have the following:

1. The main effect of A_1 is $2\beta_1$ (i.e., the main effect of clinic-level nudges averaging over the differential effects of standard and intensive texting).
2. The main effect of A_2 given $A_1 = 1$ is $2\beta_2$. This is the comparison of text messaging intensity (standard versus intensive) given clinic-level nudges are active.
3. The comparison of clinic-level nudges with intensive texting versus control is $2\beta_1 + \beta_2$.
4. The comparison of clinic-level nudges with standard texting versus control is $2\beta_1 - \beta_2$.

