We will test each of the four linear contrasts of the parameters estimated from the GEE model. We will use a Bonferroni correction for the first two contrasts, aligning with how the study was powered (i.e., two-sided significance level of 0.025 for the first two contrasts). We will consider contrasts 3 and 4 as exploratory, and thus we will not correct the corresponding p-values for multiple testing. Results will be reported on the odds ratio scale, including 95% confidence intervals. Confidence intervals for contrasts 1 and 2 will incorporate the Bonferroni correction used for the two tests.

Sensitivity Analyses to Evaluate Model Specifications

As a sensitivity analysis, we will restrict the data to high-risk patients at active clinics and estimate the main effect of intensive vs standard text messaging, specifying an exchangeable working

correlation within clinics. As another sensitivity analysis, we will use an exchangeable working correlation at the clinic level after duplicating each clinic's data, assigning one 1 and one -1 for patients without an individual-level assignment, and removing the record for each high-risk patient an intervention clinic corresponding to the opposite of the individual-level randomized assignment that was received. Duplicated clinics will be treated as independent while observations within clinic will be treated as exchangeable. In this way, duplicated records will be treated as independent. Using this approach, we will re-test the main effect of A_1 , i.e., $2\beta_1$, to evaluate sensitivity to specification of the working correlation. We will use a t-distribution with degrees of freedom equal to the number of clinics (47) minus the number of mean model parameters to construct a confidence interval for $2\beta_1$. If the interval does not include 0 (log odds ratio scale) we will reject the null and conclude there is a significant effect of clinic nudges compared to usual care.

Sensitivity Analyses to Evaluate Protocol Deviations

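### The main test (clinic nudges versus usual care) uses no small-cluster correction with about 15 control clinics, which roughly doubles its nominal 0.025 type I error

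*SAP*

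**What the plan says.** The SAP's section on randomization states: "Primary care clinics will be randomized 2:1 to either a nudge intervention or usual care arm". Its analytical plan for primary and secondary outcomes fits one weighted-and-replicated logistic GEE with independence working correlation, model (1). The covariate vector is one "which will at minimum include mean-centered versions of the three variables used in the constrained randomization procedure": clinic size, baseline risk and baseline completion rate. Protocol section 9 adjusts for health system as well.

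Contrast 1, the clinic-level nudges against usual care, is 2β₁. It is tested at a "two-sided significance level of 0.025 for the first two contrasts", and its confidence interval carries the same Bonferroni adjustment. On small-sample behaviour the SAP says: "Since we will randomize 45 clinics, we will not use a small cluster correction".

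The SAP names neither the variance estimator nor the reference distribution for this test. Protocol section 9 (Statistical Analysis) says of the clinic-level comparison that "robust standard errors will be provided, clustered at the clinic level". The only small-sample allowance is in a sensitivity analysis with exchangeable working correlation: "We will use a t-distribution with degrees of freedom equal to the number of clinics (47) minus the number of mean model parameters".

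**The concern.** Contrast 1 compares clinics, so its information comes from the number of clinics per arm and not from the number of patients. Three features each pull the uncorrected sandwich variance down or make the shortfall matter more:

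- the smaller arm has about 15 clinics;
- at least three clinic-level covariates use up clinic-level information;
- the test sits further into the tail than usual, at 0.025 rather than 0.05.

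The decision to omit a correction looks only at the total of 45.

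At stake are the type I error and interval coverage of the trial's main comparison, and the purpose of splitting alpha between two contrasts. The SAP uses the same approach for the secondary outcome. It also refits the models separately for Penn and UW, where there are fewer control clinics still; those refits were not simulated.

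**Working it through.** **Inputs from the documents.** Two-sided alpha 0.025. 45 clinics at 2:1, hence 30 and 15; the 47 in the SAP's sensitivity analysis gives about 31 and 16. Three clinic covariates, or four with health system. Mean of 1385 patients per clinic, ICC 0.02, and 1000 of 1385 patients at high risk (Protocol section 9, Power Calculations).

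**Assumed, because the documents do not say.** Null completion rate 40%; clinic sizes equal, or lognormal with CV 0.5 or 0.8; two-thirds of clinics in one health system; stratified constrained allocation drawn from the best 10% of 200 candidates.

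**The plan's own figure first.** The protocol states: "we will have 85% power to detect a 7-percentage point difference in the flu vaccine completion rate for comparison #1". The control rate is not given; 35% versus 42% reproduces the figure.

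- Design effect: 1 + 1384 × 0.02 = 28.68.
- Effective sample sizes with 32 and 16 clinics: 16 × 1385 / 28.68 = 772.7 control and 1545.3 intervention.
- SE = √(0.35 × 0.65 / 772.7 + 0.42 × 0.58 / 1545.3) = 0.02126.
- Power = Φ(0.07 / 0.02126 − 2.241) = 85.3%.
- With 30 and 15 clinics the same steps give 82.8%.

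This is a large-sample normal calculation and makes no allowance for the number of clinics.

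**Mechanism.** If the estimated SE averages a fraction r of the true sampling SD, the actual error is roughly 2Φ(−2.241r). In the simulations r ran from 0.82 to 0.93 across the size settings. That gives 0.037 at r = 0.93 and 0.066 at r = 0.82, before allowing for sampling variability in the SE itself, which adds more.

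**Simulation of model (1).** Effect-coded A₁ and A₁A₂; replicated rows at weight 1 and randomized high-risk rows at weight 2; independence logistic GEE; sandwich clustered by clinic. There were 8,004 null trials per setting (Monte Carlo SE about 0.002). The t reference uses clinics minus 5 clinic-level parameters (6 with health system). Ranges cover 30/15 and 31/16 clinics, with and without health system.

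| Variance and reference | Equal sizes | CV 0.5 | CV 0.8 |
|---|---|---|---|
| Uncorrected, normal | 0.046–0.052 | 0.057–0.060 | 0.067–0.082 |
| Uncorrected, t | 0.038–0.044 | 0.049–0.051 | 0.057–0.070 |
| Kauermann-Carroll, t | 0.029–0.031 | 0.031–0.034 | 0.034–0.042 |
| Mancl-DeRouen, normal | 0.021–0.027 | 0.021–0.027 | 0.021–0.027 |
| Mancl-DeRouen, t | 0.018–0.022 | 0.018–0.022 | 0.018–0.022 |

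For the Mancl-DeRouen rows the range is the one across all size settings.

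**Separate check.** An independently written simulation, with 40,000 trials per main setting and null rates of 0.45 and 0.30, gave 0.045–0.052 for the uncorrected adjusted test at equal sizes. With three covariates it gave 0.053, 0.058 and 0.064 at size CV 0.4, 0.6 and 0.8. With no covariates it gave 0.037. Using 47 or 48 clinics changed little (0.045–0.046).

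**Overall error for contrasts 1 and 2.** The intended value is 1 − 0.975² = 0.049. If contrast 2 held exactly 0.025, the overall error would be 1 − (1 − a) × 0.975, where a is the contrast 1 error. That is 0.070 at a = 0.046 and 0.105 at a = 0.082. Simulated with contrast 2 also uncorrected (its own error was 0.028–0.039), the overall error is 0.074–0.078 at equal sizes, 0.083–0.091 at CV 0.5 and 0.097–0.112 at CV 0.8.

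**The case against.** The strongest reply is that the size of the problem depends on details the documents leave open. No reference distribution is stated for the primary test, and with a t reference the equal-size error is 0.038–0.044. The protocol sentence on clinic-clustered standard errors was written for an exchangeable model, not for model (1). No document gives a clinic-size CV, so every figure above the equal-size column is illustrative. The omission was a deliberate, referenced choice. The practical effect is also bounded: widening the interval by 13–17% moves the critical value from 2.24 to between 2.53 and 2.62. At equal sizes, then, only an uncorrected p-value between roughly 0.009–0.011 and 0.025 would change the conclusion. The point estimate does not move.

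Much of this is fair, and it limits the size of the claim. It does not remove the defect. Declining a small-cluster correction makes sense only for a clinic-clustered variance. A normal reference is the natural reading, since the SAP refuses a correction here and gives a t only to a sensitivity analysis. Even with t, the test exceeds 0.025 at equal sizes, the most favourable case. The sensitivity analysis names no variance correction and is not the primary test. It was not simulated in its exchangeable form, so nothing is claimed about its error.

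**Conclusion.** The plan is wrong as written. With equal clinic sizes, the planned covariates and a normal reference, the actual error of contrast 1 is about 0.046–0.052 against a nominal 0.025. Its nominal 97.5% interval then covers about 95%. Unequal clinic sizes make this worse. Some inequality is to be expected, since the SAP balances and adjusts for clinic size, but the extent is not documented. The finding does not depend on whether 45, 47 or 48 clinics is correct. It does depend on the clinic-level adjustment the SAP commits to: without covariates the inflation is smaller (0.037). A strong result would survive correction; a borderline one might not, so the method has to be fixed in advance.

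**What to change.** Replace the sentence declining a correction with one that names, for contrast 1, a bias-corrected clinic-clustered variance and its reference distribution. Mancl-DeRouen with a normal reference, or with t on clinics minus clinic-level parameters (slightly conservative), holds the level here. Another correction is acceptable if shown to do so; a t reference alone is not enough.

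Confirm the choice by simulation on the real clinic sizes before unblinding. Baseline sizes exist ("Panel size is defined as the number of patient visits from September 1, 2022 through February 28, 2023"), although they count visits and so only approximate the numbers of patients analysed. State one clinic count throughout. Restate the power figure under the chosen method; the SAP reports deviations during the intervention, so this serves interpretation rather than design.

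The change is SAP wording and a standard software option, but it costs precision. The contrast 1 interval widens by 13–17% (equal sizes), 18–22% (CV 0.5) or 23–28% (CV 0.8) with Mancl-DeRouen and a normal reference. With t the figures are 17–21%, 22–27% and 27–34%.

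Simulated power for 35% versus 42% (30/15 clinics, covariates not prognostic, 4,004 trials):

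| Method | Equal sizes | CV 0.5 | CV 0.8 |
|---|---|---|---|
| Uncorrected | 84–85% | 80–81% | 77% |
| Mancl-DeRouen, normal | 76% | 67–68% | 58–60% |
| Mancl-DeRouen, t | 73% | 64% | 54–56% |

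Much of this loss is the removal of false precision. If a covariate such as baseline completion explained 30% of clinic variance (assumed), Mancl-DeRouen with a normal reference would keep 90%, 81–84% and 72–73%.

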Sensitivity analyses (described later) will include per-protocol and other approaches to evaluate robustness to protocol deviations for some patients.

Analytical Plan for Primary and Secondary Outcomes

The primary analysis will fit generalized estimating equations (GEE) with a patient-level binary outcome indicating flu vaccination completion at the eligible primary care visit (primary outcome) and within 3 months (secondary outcome) of the eligible visit. We will fit a single GEE model to estimate the following: 1) effect of the clinic-level intervention (pended orders) only versus usual practice (main effect averaging over individually randomized bi-directional versus standard texting for high-risk patients at intervention clinics), and 2) effect of bi-directional vs standard text messaging amongst high-risk patients seen at intervention clinics, and 3) effect of the multicomponent intervention (pended orders and intensive texting for high-risk patients) compared to usual practice. These effects of interest are analogous to comparisons of intervention sequences embedded within Sequential Multiple Assignment Randomized Trial (SMART) designs. Therefore, we will adapt statistical methods commonly used for the analysis of data from SMART designs and use them to analyze data from the trial. More specifically, we will adapt the weighted and replicated approach that is used to compare embedded treatment sequences in SMART designs.¹

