The weighted and replicated method is an analytic trick that allows for standard statistical software to be used to fit a single model for statistical estimation and inference regarding multiple effects of interest. Only high-risk patients seen at active intervention clinics are randomized to standard or intensive text messaging. Low-risk patients and all patients seen at control clinics are only exposed to the clinic-level randomized assignment. As a result, they do not have an individual-level randomized assignment in the analytic data set. To fit a single model, we must assign these individuals a value for the individual-level randomization. To do so, we first replicate their row of data and assign one of their records to standard messaging and the other to intensive messaging. However, after replicating these individuals, they will be over-represented in the analytic data set compared to high-risk, intervention clinic patients who received an individual-level randomized assignment and are therefore not replicated. To re-balance the representation in the pseudo-population created by replicating some patient observations, we weight each row by the inverse of the probability of receiving the observed value of the individual-level intervention. That is, patients who were truly randomized to standard or intensive texting will receive a weight of 2 (inverse of $\frac{1}{2}$) while each row of a patient whose record was replicated will receive a weight of 1 (since their intervention “assignments” were deterministic).

Once the replicated data set is created, we will fit the following GEE model to the patient-level binary outcomes using the observation weights mentioned above:

$$\text{logit} (\Pr(Y = 1 | A_1, A_2, X)) = \beta_0 + \beta_1 A_1 + \beta_2 A_1 A_2 + \beta_3^T X, \quad (1)$$

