To examine the effect of the intervention on flu vaccination ordering, a GEE with a binary outcome indicating whether the pended order was signed or cancelled will be fit. The rates of flu vaccination completion will be compared between (1) usual care, (2) clinic level nudge only, and (3) clinic-level nudges with high-risk intensification using the same weighted and replicated approach described for the primary outcome and the mean model given in equation (1). We will again use an independence working correlation for these comparisons and perform sensitivity analyses to assess sensitivity to specification of the working correlation.

Exploratory subgroup analyses will examine the effect of the clinic-level nudge versus usual care among patients who are 1) identified as low-risk for completion and 2) identified as high-risk for completion, and 3) seen at Penn versus UW. For (1), we will restrict the data set to low-risk patients in the active and control clinics. Then, we will fit a GEE model with an indicator for clinic randomized assignment and variables used in the covariate constrained randomization. We will fit the model with a logit link and exchangeable working correlation. For (2), we will subset the data to patients deemed high-risk in both active and control arms, we will fit a GEE model with an indicator for clinic randomized assignment, indicator for individual-level randomized assignment, interaction between the clinic- and individual-level randomized assignments, and variables used in the covariate constrained randomization. We will use the weighted and replicated approach described previously, replicating each high-risk patient in the control arm and assigning them each a weight of 1 while assigning each high-risk patient in the

intervention clinics a weight of 2. We will fit the model with a logit link and independent working correlation. We will test the main effect of the clinic-level nudge and the main effect of standard versus intensive texting. We will test contrasts 1), 3), and 4). For investigating possible effect heterogeneity by health system, we will re-fit models for our primary and secondary outcomes separately on data from Penn and UW.

To investigate potential effect heterogeneity over time, we will fit GEE models for our primary and secondary outcomes with the addition of month and month-by-treatment interactions. The model will take the following form:

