$$\text{logit} (\Pr(Y = 1 | A_1, A_2, T, X)) = \beta_0 + \beta_1 A_1 + \beta_2 A_1 A_2 + \beta_3 T + \beta_4 A_1 T + \beta_5 A_1 A_2 T + \beta_6^T X, \quad (2)$$

where T is a categorical variable indicating study month. We will use the weighted and replicated approach and an independent working correlation structure. We will first assess whether the effect of text messaging style differs over time. If we do not find evidence of effect heterogeneity for text messaging style, we will drop A_2 from the model and focus only on the effect of pended orders over time using the following model:

$$\text{logit} (\Pr(Y = 1 | A_1, A_2, T, X)) = \beta_0 + \beta_1 A_1 + \beta_2 T + \beta_4 A_1 T + \beta_5^T X, \quad (3)$$

Inference will focus on the interaction effect, β_4 , and we will not use any weighting or replicating to fit this model. We will fit this model using an independent working correlation.

Lastly, we will determine which high-risk intensification subgroups experienced the greatest benefits of the clinic- and individual-level nudges. Using the data set restricted to high-risk individuals, we will fit the following model:

$$\text{logit} (\Pr(Y = 1 | A_1, A_2, Z, X)) = \beta_0 + \beta_1 A_1 + \beta_2 A_1 A_2 + \beta_3 Z + \beta_4 A_1 Z + \beta_5 A_1 A_2 Z + \beta_6^T X, \quad (4)$$

where Z is a single, high-risk criteria. We will fit model (2) separately for each high-risk criteria which will allow us to determine which high-risk intensification subgroups experienced the greatest benefits of the clinic- and individual-level nudges. We will again use the weighted and replicated approach,

duplicating each control arm patient and assigning them a weight of 1 while assigning each intervention clinic patient a weight of 2. We will use an independent working correlation structure.

We now provide details about the interaction effects of interest. First, note that the main effect of A_1 amongst $Z = 1$ is:

$$\begin{aligned}\beta_0 + \beta_1 + \beta_2 A_2 + \beta_3 + \beta_4 + \beta_5 A_2 + \beta_6^T X - (\beta_0 - \beta_1 - \beta_2 A_2 + \beta_3 - \beta_4 - \beta_5 A_2 + \beta_6^T X) \\ = 2\beta_1 + 2\beta_4\end{aligned}$$

Similarly, the main effect of A_1 amongst $Z = 0$ is:

$$\begin{aligned}\beta_0 + \beta_1 + \beta_2 A_2 + \beta_6^T X - (\beta_0 - \beta_1 - \beta_2 A_2 + \beta_6^T X) \\ = 2\beta_1\end{aligned}$$

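### Contrast 2 (2β2 of SAP model 1) does not estimate the texting effect in high-risk patients; on the planning figures it returns about 48% of that log odds ratio

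*SAP*

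**What the plan says.** In the SAP, Analytical Plan for Primary and Secondary Outcomes, the second effect to be estimated is the "effect of bi-directional vs standard text messaging amongst high-risk patients seen at intervention clinics". Only those patients are randomised to a texting style. For low-risk patients and all control-clinic patients the SAP says: "we first replicate their row of data and assign one of their records to standard messaging and the other to intensive messaging". Each replicated row has weight 1 and each randomised patient weight 2.

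Model (1) is then fitted to all rows. Clinic assignment A1 and texting A2 are both coded +1/−1. A2 enters only through the product A1·A2, with coefficient β2. The contrast list below the model gives 2β2 as the effect of A2 when A1 = 1 and adds: "This is the comparison of text messaging intensity (standard versus intensive) given clinic-level nudges are active". Contrasts 1 and 2 are each tested at two-sided 0.025 and reported as odds ratios. "Confidence intervals for contrasts 1 and 2 will incorporate the Bonferroni correction used for the two tests".

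Under Sensitivity Analyses to Evaluate Model Specifications, the SAP also plans this: "we will restrict the data to high-risk patients at active clinics and estimate the main effect of intensive vs standard text messaging".

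The protocol (section 9, Power Calculations) powers the texting comparison on high-risk patients alone, assuming "1:1 individual-level randomization of n=1000 high-risk patients within each of N=32 clinics". Its Statistical Analysis text puts clinic fixed effects in the model for intensification.

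**The concern.** A patient who appears once at A2 = +1 and once at A2 = −1 with the same outcome carries no information on texting. In model (1) such patients are nevertheless fitted with the same β2 as the randomised patients, so 2β2 averages the true effect with many built-in zeros.

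The product coding adds a second problem. With A1 = −1, the term A1·A2 gives control clinics a texting effect of −2β2, although no control patient was randomised to texting. The data there show zero, which pulls β2 down further.

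At stake is the published effect size for one of only two alpha-controlled comparisons, the one that answers the protocol's second objective. The planned high-risk-only sensitivity analysis would show a log odds ratio about twice as large. That gap would be read as sensitivity to the working correlation, when the coding causes it.

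**Working it through.** **Plan's own figures.** The SAP gives no figure for the dilution. The protocol gives at least 99% power for a 2-point difference at a 50% rate. With 16,000 per arm and two-sided 0.025, 50% versus 52% gives 91%. It exceeds 99% (99.8%) only with 1,000 per arm per clinic, which does not fit an average clinic of 1,385. The point below does not depend on this.

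**Inputs** (protocol section 9, Power Calculations; 2:1 allocation of 48 clinics):
- randomised high-risk patients: nH = 32 × 1,000 = 32,000
- low-risk patients at intervention clinics: nL = 32 × 385 = 12,320
- control patients: nC = 16 × 1,385 = 22,160

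**Closed form.** Let δ be the true log odds ratio among randomised high-risk patients. Each patient carries total weight 2. With similar outcome rates in all groups, the score equation for β2 is

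nH(δ − 2β2) − 2β2(nL + nC) = 0, so 2β2 = δ · nH/(nH + nL + nC).

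The factor is 32,000/66,480 = 0.481.

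**Numerical check.** Solving the weighted logistic score on expected cell counts gives 0.48 to 0.49 with the high-risk rate at 50%, assumed low-risk rates of 40% to 60% and control rates of 43% to 53%. The clinic-level covariates in X were left out because they are balanced over A2 within clinic.

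**Where the loss arises.**
- Low-risk rows alone: 32,000/44,320 = 0.72. This is what remains if the texting term is set to 0 in control clinics.
- Control rows alone, on high-risk data: 32,000/48,000 = 0.67.
- Together: 0.72 × 0.67 = 0.48.

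**By assumed high-risk share** (2/3 × share): 0.33 at 50%, 0.48 at 72.2% (planning), 0.67 at 100%. With the SAP's 45 or 47 clinics and the planning share the factor stays 0.48 to 0.49.

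**Effect on the report.** For 49% versus 51%, δ = 0.0800 (odds ratio 1.083). The reported log odds ratio is 0.481 × 0.0800 = 0.0385, an odds ratio of about 1.04.

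**Coverage of δ by the 97.5% interval.** SE(δ) = √(2/(16,000 × 0.25)) = 0.0224, the SE of 2β2 is 0.481 × 0.0224 = 0.0108, and the critical value is 2.241. The simulation used 2,000 trials per setting, ICC 0.02, rates of 50% and 43%, and clinic-clustered standard errors.

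| True difference | Normal approximation | Simulation |
|---|---|---|
| 2 points | 5% | 8% |
| 1.5 points | 26% | 27% |
| 1 point | 62% | 60% |
| 0.5 points | 90% | 89% |

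A second simulation (1,000 trials) gave a mean 2β2 of 0.0387 and 10% coverage at 2 points. The clinic-stratified estimate from high-risk patients only averaged 0.0797 against 0.0800, with 97.3% coverage.

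**Test.** When δ = 0, β2 = 0. Simulated rejection with clinic-clustered errors was 3.0% to 3.2% (nominal 2.5%). Power at 2 points was 89% to 91%, against 91% for the direct comparison. It would be about 79% if replicated rows were treated as independent.

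**Other models.**
- Contrasts 3 and 4 barely move (control assumed 43%): 1.352 instead of 1.364, and 1.300 instead of 1.288.
- Model (2) carries the same term.
- Model (4) uses high-risk data but is built by "duplicating each control arm patient and assigning them a weight of 1 while assigning each intervention clinic patient a weight of 2", so its texting effect and 2β5 shrink to about 0.67.
- The exploratory high-risk subgroup model has an "indicator for individual-level randomized assignment, interaction between the clinic- and individual-level randomized assignments". Under ±1 coding, each of those two terms alone gives δ/2; their sum gives δ.

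**The case against.** The strongest reply is that the inference survives. The null test is valid, power is nearly unchanged, the error runs towards an odds ratio of 1 and so cannot create a false claim of benefit, and the SAP already plans the correct high-risk analysis as a sensitivity check. All of that is true. It does not repair the odds ratio and interval that the SAP commits to report for this comparison.

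A second reply is that the SAP likens its effects to SMART sequence comparisons, and the contrast list does not repeat the words high-risk. If contrast 2 meant all patients at intervention clinics, averaging over low-risk patients would be part of the target. The correct factor would be 0.72, and 2β2 would still be about one third too small. Coverage of that target would be about 67% at 2 points and 91% at 1 point. This reading softens the result, but it conflicts with the SAP's own definition of the effect.

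Third, the factor depends on outcome rates that the documents do not give. Less central assumed rates give 0.41 (high-risk 20%, low-risk 50%, control 20%) to 0.51 (50%, 70%, 30%), and extreme ones 0.38 to 0.58. So 0.48 is a central value, not an exact one.

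Fourth, the 79% power figure is remote. The SAP's remark on small-cluster correction implies clustering by clinic, although it never names the level.

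**Conclusion.** The concern holds. Contrast 2 as specified does not estimate the effect that the SAP names. On the planning counts and rates near 50% it gives about 0.48 of the log odds ratio, and under every set of rates tried it stays well below 1. The practical damage depends on the true effect: interval coverage is close to nominal at 0.5 points, falls below half above about 1.2 points, and is 5% to 10% at the 2 points used for powering. The error concerns the estimate and interval, not the test, provided both copies of a patient stay in one clinic cluster. The SAP's argument that GEE estimates tolerate a wrong working correlation does not help, because the fault is in the mean model. Adding a risk-group indicator to X would not help either, since the dilution comes from the single A1·A2 term. This must be corrected before the contrast is reported.

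**What to change.** 1. Estimate contrast 2 from the randomised high-risk patients at intervention clinics only, in a model with A2 and clinic fixed effects, as protocol section 9 (Statistical Analysis) states. Keep the exchangeable-correlation version as its sensitivity analysis.
2. In models (1), (2) and (4), replace A1·A2 by a term equal to A2 in intervention clinics and 0 in control clinics. The formulas 2β1 + β2 and 2β1 − β2 for contrasts 3 and 4 do not change.
3. For any texting effect in high-risk patients taken from model (2), also restrict the data to high-risk patients, because recoding alone leaves a factor of about 0.72.
4. In the exploratory high-risk subgroup model, define the texting effect as the sum of the A2 and A1·A2 effects.
5. State that robust standard errors are clustered by clinic, with both copies of a patient in the same cluster.

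The first change is the essential one. The cost is SAP wording and one extra model fit, with no change to data or design. The drawback is that contrasts 1 and 2 no longer come from a single model.
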